12.1 Definitions / Classifications

Adverse Event (AE):

Any untoward medical occurrence, unintended disease or injury or any untoward clinical signs or symptoms (including abnormal laboratory value, or other medical event) in subjects, whether or not related to study medication. Physical findings (including vital signs) observed at follow-up, or pre-existing physical findings that worsen compared to baseline, are adverse events if the investigator determines they are clinically significant.

NOTE: Specifically for drug-related AEs (adverse drug reaction; ADR) the following definition applies: Regarding marketed medicinal products, a drug-related AE or adverse drug reaction is a response to a drug which is noxious and unintended and which occurs at doses normally used in man for prophylaxis, diagnosis, or therapy of diseases or for modification of physiological function. All drugs taken per protocol requirements will be considered for AE reporting.

NOTE: AF recurrence by itself is considered a recurrence of disease (pre-existing condition) and therefore does not meet the definition of an AE, unless it is a worsening compared to the preexisting condition; and unless AF recurrence meets at least one of the conditions for an SAE.

Serious Adverse Event (SAE):

A SAE is an event that:

- Lead to a death.
- Lead to a serious deterioration in the health of a subject that:
 - resulted in a life-threatening illness or injury;
 - resulted in a permanent impairment of a body structure or a body function;
 - required in-patient hospitalization or prolongation of existing hospitalization; or
 - resulted in medical or surgical intervention to prevent permanent impairment to body structure or a body function.
- Led to foetal distress, foetal death or a congenital abnormality or birth defect.

NOTE: A planned hospitalization for a pre-existing condition (without serious deterioration in health) is not considered a serious adverse event. An AE would meet the criterion of "hospitalization", if the event necessitated an admission to a health care facility (eg, overnight stay). Emergency room visits that do not result in admission to the hospital should be evaluated for one of the other serious outcomes.

Unanticipated Adverse Event:

An unanticipated AE is a serious event not previously identified in nature, severity or degree of incidence, or any other unanticipated serious problem associated with the commercially approved OAT that relates to the rights, safety or welfare of subjects.

Adverse Events (AE) associated with OAT can be found in the package insert for commercially approved drugs (listed under Adverse Reactions). AEs deemed related to OAT that are not found within the package insert will be considered unanticipated AEs.

Anticipated Adverse Events:

All AEs listed in the package insert for a subject's prescribed OAT will be considered anticipated adverse events for purposes of this study.

12.2 Causality

Regarding the causality of each OAT-related AE, the investigator will assess and evaluate the causality of the AE as related to the use or discontinuation of OAT according to the following classifications:

Table 4: Adverse Event Causality Classifications

Definitely	The drug directly caused or contributed to the AE
Probably	The drug likely caused or contributed to the AE
Possibly	The drug may have caused or contributed to the AE
Not Related	The drug did not cause or contribute to the AE

12.3 Intensity / Severity

Regarding the intensity/severity of each AE, the investigator will assess and evaluate the relationship according to the following definitions:

Table 5: Adverse Event Intensity or Severity Definitions

Mild	Any event that results in minimal transient impairment of a body function or damage to a body structure, and/or does not require intervention other than monitoring.
Moderate	Any event that results in moderate transient impairment of a body function or damage to a body structure, or that requires intervention, such as the administration of medication, to prevent permanent impairment of a body function or damage to a body structure.
Severe	Any event that is life threatening and results in permanent impairment of a body function or damage to a body structure, or that requires significant intervention, such as major surgery, to prevent permanent impairment of a body function or damage to a body structure.

12.4 Outcome

Regarding the outcome of each AE, the investigator will assess and evaluate the relationship according to the following classifications:

Table 6: Adverse Event Outcome Classifications

Classification	Definition
Resolved without sequelae	Subject fully recovered with no observable residual effects
Resolved with sequelae	Subject recovered with observable residual effects
Improved	Subject's condition improved, but residual effects remain
Unchanged	AE is ongoing
Worsened	Subject's overall condition worsened
Death	Subject died as a result of the AE

12.5 Adverse Event Documentation and Reporting Requirements:

AE information will be collected throughout the study and will be recorded on eCRFs. The investigator is responsible for ensuring that all AEs observed by the investigator or reported by the subject that occur from the time that the subject has signed the informed consent through the end of the study are properly assessed, recorded, and reported as defined and described in the Adverse Events Section (12.0) of this protocol. All AEs must be assessed by the study investigator and properly documented by completing the subject's medical records (source documents) and appropriate eCRF. Additional documentation may be requested by the Sponsor, including but not limited to, a written subject narrative detailing the clinical course of the AE, a copy of any correspondence with the local EC/EB, and extracts from medical records (patient identifiers removed). All AEs will be monitored until they are adequately resolved or explained.

Table 8: AE Reporting Requirements

Type of Adverse Event	Reporting Requirements
Non-Serious and Anticipated Adverse Events	Report to Sponsor within 7 days of awareness
Serious Adverse Events	Report to Sponsor within 24 hours of awareness
Unanticipated AEs	Report to Sponsor within 24 hours of awareness
Subject Death	Report to Sponsor within 24 hours of awareness

The Sponsor will confirm that (serious) AEs are reported as required to the:

- **To Institutional Review Board (or equivalent):** The site is responsible for ensuring that all (serious) AEs are fully recorded and reported to the IRB (or equivalent) according to the local requirements.
- **To Global Safety Monitoring Committee (GSMC):** The sponsor will forward all reported SAEs to the GSMC. The GSMC will evaluate whether the event is unanticipated, the seriousness, the relationship with/to the OAT (as applicable), and the perceived risk for the other study centers. The GSMC will determine whether the event is drug-related. Additional detail regarding the GSMC is provided in the Study Management Section (15.0) of this protocol.

13.0 Statistical Analysis Plan

13.1 Study Objective

The objective of this study is to assess whether the patients who discontinued OAT after a successful AF ablation are not inferior to the group of patients who continued OAT after a successful AF ablation in terms of the composite endpoint of all ischemic and hemorrhagic events.

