5.0 Introduction

5.1 Background

Atrial fibrillation (AF) is the most common sustained cardiac arrhythmia, with a prevalence of between 0.9% and 2.5% in the general population and an increasing incidence with age.^{2,3} This arrhythmia is associated with an increased risk of thromboembolic complications and in particular of ischemic stroke. The rate of this complication varies from fewer than 2 to more than 10 strokes per 100 patient-years without antithrombotic therapy.^{4,5} The stroke risk increases in the presence of cardiovascular diseases, such as rheumatic mitral stenosis, or prosthetic cardiac valves. Furthermore, patients with non-valvular AF, a history of previous thromboembolism, advanced age, hypertension, diabetes mellitus, and heart failure have an increased risk of stroke.⁶ Thromboembolic complications generally result from left atrium thrombi, the left atrial appendage (LAA) being the most common source of thrombus formation, with an incidence of 91% in patients with non-valvular AF.^{6,7} The pathogenesis of LAA thrombi has not been fully elucidated, but the relative stasis of the blood within the appendage, due to its anatomy and altered function during AF (reduced contraction, filling dynamics), is thought to play a major role.⁸

Adjusted-dose warfarin is highly effective in preventing stroke, and reduces risk by 62% versus placebo in patients with non-valvular AF;⁹ however, it increases the risk of major bleeding by 1.2% per year.⁶ The absolute reduction in stroke risk is reported to be 2.7% per year for primary prevention and 8.4% per year for secondary prevention.⁹

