6.0 Study Hypothesis

High risk subjects who have successful cardiac ablation and remain free from AF recurrence for 3 months post ablation procedure can discontinue their OAT without an increased risk of thromboembolic events as compared to those who remain on OAT.

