7.0 Objective

The objective of this study is to determine the safety of discontinuing oral anticoagulation therapy in high risk patients who have had a successful cardiac ablation and remain AF recurrence free for 3 months post ablation.

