13.3 Sample Size

A total sample size of 100 (50:50) subjects will be enrolled in this pilot study. This is a pilot study and is not statistically powered to make a statistical inference.

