13.4 Analysis Population

The study contains two treatment arms with subjects either discontinuing OAT or continuing OAT. The primary analysis will be based on the intent-to-treat principle where subjects will be analyzed by the group to which they are randomized, regardless of actual treatment received. Lost-to-follow-up, discontinued, and withdrawn / early termination subjects will also be included in this analysis.

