13.7 Endpoint Analyses

13.7.1 Primary Endpoint Analysis

The primary endpoint is the occurrence of any thromboembolic event or major hemorrhagic complications during the 12-month Evaluation Period.

The Kaplan-Meier method will be used to model the time to the first occurrence of any thromboembolic event or major hemorrhagic complications during the 12-month Evaluation Period following randomization. The survival probabilities of the occurrence of any thromboembolic event or major hemorrhagic complications at the 12 month follow-up along with the corresponding 95% confidence intervals will also be presented. The equality of the survival curves between two randomization groups will be tested by the Log-rank test.

This analysis will include all subjects in the analysis population and account for censored observations. Subjects lost to follow-up, withdrew or discontinued prior to reaching their primary endpoint will be censored at their last visit.

Descriptive statistics such as 25th percentile, median and 75th percentile of time to the first occurrence as well as the 95% confidence intervals around the median time will be presented overall and by randomization groups.

The number and proportion of subjects experiencing occurrence of any thromboembolic event or major hemorrhagic complications will be summarized overall and by two randomization groups at 12 month follow up. The Fisher exact test will be used to compare the proportions between the two randomization groups.

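### The stated objective is non-inferiority, but the arms are compared only by tests of equality, with no margin and no between-arm confidence interval

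*Combined protocol and SAP*

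**What the plan says.** All references are to the combined protocol and SAP.

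- **Objective.** Section 13.1 sets out to assess whether "patients who discontinued OAT after a successful AF ablation are not inferior to the group of patients who continued OAT", judged on the composite of ischemic and hemorrhagic events. Section 7.0 is worded differently: "The objective of this study is to determine the safety of discontinuing oral anticoagulation therapy in high risk patients".
- **Hypothesis.** Section 6.0, repeated in the Section 3.0 summary, covers thromboembolic events only. It says that high-risk subjects "can discontinue their OAT without an increased risk of thromboembolic events as compared to those who remain on OAT".
- **Between-arm comparison of the primary endpoint.** Section 13.7.1 names two tests: "The equality of the survival curves between two randomization groups will be tested by the Log-rank test", and "The Fisher exact test will be used to compare the proportions between the two randomization groups". Its 95% confidence intervals are for the 12-month survival probabilities and the median times to event. Section 13.7.2 gives intervals overall and by group.
- **Sample size.** Section 13.3 plans 100 subjects, 50 per arm, and adds: "This is a pilot study and is not statistically powered to make a statistical inference".
- **Analysis set.** Section 13.4 applies intention-to-treat and says: "Lost-to-follow-up, discontinued, and withdrawn / early termination subjects will also be included in this analysis".

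The plan states no non-inferiority margin, alpha level, hazard ratio or interval for a risk difference.

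**The concern.** A non-inferiority question asks whether an excess risk of a given size can be ruled out. That takes a contrast between the arms, an interval around it and, for a formal claim, a margin. The log-rank and Fisher tests ask whether the data contradict equal risk. Failure to reject equality can mean that the arms are alike, or that there were too few events to tell. With 50 per arm and a rare endpoint, the second reading is the likely one.

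The risk is that a non-significant result is read as evidence that stopping OAT is safe. Nothing in the plan rules out that reading, and the objective invites it. The quantity that would inform the objective, and help to plan a pivotal trial, is the difference in 12-month risk with its uncertainty. It is not pre-specified.

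A lesser point concerns the Fisher comparison. Section 13.7.1 names no denominator for its proportions. If all randomized subjects are used, as Section 13.4 suggests, subjects who leave early without an event count as event-free for the full 12 months.

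**Working it through.** The sample size of 100 cannot be reproduced, because no event rate, effect, margin, alpha or power is given for it. The check therefore asks how the planned tests would behave at 50 per arm.

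**Inputs from Section 5.1**
- Warfarin reduces stroke by 62%. "The absolute reduction in stroke risk is reported to be 2.7% per year for primary prevention and 8.4% per year for secondary prevention".
- Warfarin adds 1.2% per year to the risk of major bleeding.
- Major hemorrhage on OAT runs from 1.5 to 4.2 per 100 patient-years, depending on age.

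**Assumptions not in the plan:** two-sided alpha 0.05; full 12-month follow-up; general-AF rates carried over to this population; the same 62% reduction in both prevention strata; stroke and bleeding independent; bleeding 1.2 points lower off OAT.

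**Step 1, stroke risk.** Off OAT = absolute reduction / 0.62; on OAT = off OAT minus the absolute reduction.
- Primary prevention: 2.7/0.62 = 4.35% off, 4.35 − 2.70 = 1.65% on.
- Secondary prevention: 8.4/0.62 = 13.55% off, 13.55 − 8.40 = 5.15% on.

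**Step 2, composite risk** = 1 − (1 − stroke)(1 − bleed). Bleeding is 1.5% or 4.2% on OAT, hence 0.3% or 3.0% off OAT. First row: 1 − (0.9565 × 0.997) = 4.64% off, and 1 − (0.9835 × 0.985) = 3.13% on.

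**Step 3, chance of a significant result.** Fisher is by exact enumeration, log-rank by 20,000 simulated trials per row.

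| Scenario (bleeding on OAT) | Withdrawal vs OAT | Expected events, both arms | Fisher power | Log-rank power |
|---|---|---|---|---|
| Primary prevention (1.5%) | 4.64% vs 3.13% | 3.9 | 0.7% | 5.5% |
| Primary prevention (4.2%) | 7.22% vs 5.79% | 6.5 | 1.5% | 5.6% |
| Secondary prevention (1.5%) | 13.81% vs 6.57% | 10.2 | 12.0% | 21.7% |
| Secondary prevention (4.2%) | 16.14% vs 9.13% | 12.6 | 10.5% | 18.0% |

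Expected events = 50 × (sum of the two risks). The chance of non-significance runs from 100 − 21.7 = about 78% to 100 − 0.7 = about 99%. At primary-prevention rates the log-rank test rejects about as often as its nominal 5% level under no difference. Fisher needs 6 vs 0, 8 vs 1 or 10 vs 2 events to reach p<0.05; 5 vs 0 gives p=0.056.

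**Step 4, sensitivity**
- Stroke alone, with no offset from fewer bleeds: Fisher 1.0% and 17.1%, log-rank 8.1% and 29.7%. The low end for non-significance falls to about 70%.
- Assumed 25% early exit per arm: log-rank 4.0%, 5.4%, 19.9% and 16.4% for the four rows.
- Lower rates, such as stroke 2% vs 0.76% with bleeding 0% vs 1.2% (composite 2.0% vs 1.96%): Fisher is non-significant in 99.97% of trials.

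**Step 5, what an interval would show.** Newcombe 95% limits for withdrawal minus OAT:
- 0/50 vs 0/50: −7.1 to +7.1 points.
- 1/50 vs 1/50: −8.7 to +8.7 points.
- 3/50 vs 1/50: the Wilson limits are 2.1% to 16.2% and 0.4% to 10.5%, and the difference of 4.0 points has limits −5.4 to +14.3. Fisher gives p=0.62 for the same data.

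**Step 6, zero events.** P(at least one arm empty) = 1 − [1 − (1 − pT)^50][1 − (1 − pC)^50], where pT and pC are the risks in the withdrawal and OAT arms. This is 28% and 7% for the two primary-prevention composites, and 49.5% for primary-prevention stroke alone. The interval method must therefore cope with an empty arm.

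**Step 7, Fisher denominator.** Suppose 40% of the withdrawal arm and 20% of the OAT arm leave early, at a constant rate over the year. With true risks of 4.64% and 3.13% (difference 1.5 points), the expected crude proportions over all randomized are 3.64% and 2.81%, a difference of about 0.8 points.

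**The case against.** The strongest reply is that this is a pilot and says so. Section 13.3 disclaims statistical inference, no passage says that a non-significant p-value will be read as non-inferiority, and Section 7.0 makes no non-inferiority claim. Section 13.7.1 also provides 12-month Kaplan-Meier probabilities with intervals and event counts by arm, from which a reader could approximate a difference. On this view the fault is loose wording and one missing estimate.

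Part of this stands. Low power is conceded in the plan and is not itself the fault, and the information for a contrast will be collected. But the disclaimer sits beside an inferential objective and inferential tests and reconciles neither. A pilot that disclaims inference calls for estimation with an interval, which is the output left out.

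Three further cautions are fair.
- The 78% to 99% range rests on warfarin-era, general-AF rates. Section 5.2 reports very few thrombotic events after successful ablation, on or off OAT. Lower rates would make the tests less informative still, and the mismatch depends on no rate.
- The denominator effect in Step 7 is small beside an interval about 20 points wide, and its exit rates are assumed.
- The plan censors subjects who leave at AF recurrence, and withdrawal-arm subjects who resume OAT (Sections 9.6, 11.2.1, 11.3 and 13.7.1). That censoring may be informative and may differ by arm. A Kaplan-Meier difference inherits this weakness from the plan's own analysis and does not cure it.

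**Conclusion.** The concern holds and should be fixed. Section 13.1 poses a non-inferiority question, and no between-arm analysis in Section 13.7.1 can answer it. That conclusion comes from the text alone.

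The size is illustrative. Under the assumptions listed in the working, the planned tests would miss a true increase in stroke risk in about 78% to 99% of trials on the composite, or as few as about 70% on stroke alone at the highest rates. Even with no events in either arm, the 95% interval would reach an excess of about 7 points. The pilot can run as designed, but as written its stated question would go unanswered, and a non-significant p-value could be mistaken for reassurance.

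**What to change.** 1. **Primary between-arm output.** In Section 13.7.1, pre-specify the difference in 12-month Kaplan-Meier event risk (withdrawal minus OAT) with a two-sided 95% confidence interval from a named method that is valid when an arm has no events. One option is a Newcombe-type (MOVER) interval built from Wilson limits in each arm. The effective sample size is F(1 − F) divided by the Greenwood variance, F being the arm's Kaplan-Meier risk, or the person-years followed if the arm has no events. In simulation over nine scenarios (three composite rate pairs; early exit of 0/0, 25/25 or 40/20%) this covered 96–99%, against 91–95% for the plain Greenwood interval, which should not be used.
2. **Component.** Give the same interval for thromboembolic events alone. Section 6.0 concerns only these, and fewer bleeds off OAT can mask more strokes in the composite.
3. **Wording.** Restate Section 13.1 as estimating the difference, and align the summary (Section 3.0) and Sections 6.0 and 7.0. State that no non-inferiority or safety conclusion will be drawn from a non-significant p-value.
4. **Tests.** Label the log-rank test exploratory and drop the Fisher comparison of crude proportions for the primary endpoint. Do not replace it with a comparison limited to subjects with known 12-month status: that would keep the events and drop the event-free early exits.

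The cost is a protocol amendment approved under Section 14.5 and one additional table, with no extra patients or data. The price is a more modest objective and visibly wide intervals.

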13.2 Primary Endpoint

The primary endpoint is a composite endpoint represented by the occurrence of any major thromboembolic event (stroke [i.e., ischemic, hemorrhagic or cryptogenic] that is an acute onset of a focal neurologic deficit of presumed vascular origin lasting for ≥ 24 hours or resulting in death) or major hemorrhagic complication (major bleeding) during the 12-month Evaluation Period.

13.3 Sample Size

A total sample size of 100 (50:50) subjects will be enrolled in this pilot study. This is a pilot study and is not statistically powered to make a statistical inference.

13.4 Analysis Population

The study contains two treatment arms with subjects either discontinuing OAT or continuing OAT. The primary analysis will be based on the intent-to-treat principle where subjects will be analyzed by the group to which they are randomized, regardless of actual treatment received. Lost-to-follow-up, discontinued, and withdrawn / early termination subjects will also be included in this analysis.

13.5 Analysis by Subject Disposition

The number of subjects that are enrolled, excluded, discontinued, prematurely withdrawn from the study, and lost to follow-up will be summarized and listed by randomization group, by gender, and by study site.

13.6 Demographic and Baseline Characteristics

The descriptive statistics of demographic and baseline characteristics include but are not limited to (1) age; (2) gender; (3) race; (4) ethnicity; (5) medical history conditions; and (6) AF history and will be presented overall and by randomization group. The descriptive statistics including number of subjects, mean, median, 25th and 75th percentiles, minimum, maximum and standard deviation will be presented for continuous variables. Frequency and percentage will be presented for categorical variables. The Fisher exact test will be used to examine the categorical demographic and baseline characteristics between two randomization groups. Wilcoxon rank sum test will be used for the continuous variables.

